1.5.1 Risk Mitigation Strategy

Immunogenicity

BMS-986036 is a PEGylated recombinant variant of human FGF21 and has the potential to be immunogenic, however, the potential safety liability of antibody formation in humans is considered to be low. Most human protein therapeutics can induce a rapid and strong ADA response in animals but the presence of ADA in these species does not necessarily predict immunogenicity in humans.³⁴ Following daily dosing, BMS-986036 ADA were detected in rats and monkeys in 1-month (up to 59% and 20%, respectively) and 4-month (up to 87% and 30%, respectively) toxicology studies at all doses tested. However, the presence of ADAs in these species had no substantial or meaningful impact on the overall toxicokinetic results of total and C-terminal intact BMS-986036, pharmacodynamic, toxicology, clinical pathology or histopathology endpoints on these studies.

In the first in human study, three of 72 subjects (4%) dosed with BMS-986036 had positive results in the ADA and anti-FGF21 antibody assays at the end of study time point. Additional post-study follow-up immunogenicity testing for these three subjects showed progressively decreasing assay titers at subsequent visits over a six month time period. One of these three

subjects tested neutralizing in the neutralizing antibody assay at two out of three follow up visits. At the end of this follow up period, all 3 subjects were reported in good health with no adverse events reported.

There is a theoretical risk of neutralizing antibody formation to BMS-986036 that could cross react with endogenous FGF21. FGF21 knockout mice are known to be viable, are able to reproduce and have a generally normal phenotype.³⁵ The clinical consequences of a neutralizing anti-drug antibody (ADA) response to endogenous FGF21 are unknown, as FGF21 deficiency has not been reported in humans. Subject safety will be closely guarded in early clinical studies. All subjects administered BMS-986036 will be closely monitored for possible immunogenicity related adverse events (AEs), such as rash, fever and severe injection site reactions. Clinically relevant immune reactions (e.g. hypersensitivity reactions) considered related to BMS-986036 will be reported as AEs and treated according to current standard of care medical practice.

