3 INVESTIGATIONAL PLAN

3.1 Study Design and Duration

Study MB130045 is a randomized, double-blind, placebo-controlled, parallel-group, multiple dose design. Subjects will undergo screening evaluations to determine eligibility within 42 days prior to randomization. There will be a 7-day study skills training (Lead-In) period prior to randomization on Day 1. Eligible subjects will be randomized via IVRS on Day 1 to 1 of 3 parallel treatment groups. In total, approximately 90 randomized subjects (30 per group; ratio 1:1:1) will self-administer double-blind treatment, once daily for 16 weeks, in an outpatient setting. Subjects will be stratified using a diagnosis of Type 2 diabetes mellitus (yes vs no) based on current American Diabetes Association (ADA) criteria. Clinic visits are scheduled approximately every 2 weeks initially, and then monthly, to collect safety, PK and PD measures. The study design schematic is presented in Table 3.1-1.

Table 3.1-1: Study Design Schematic

Visit Days										
D -42 ^a	D -7	D 1	D 15	D 29	D 43	D 57	D 86 ^b	D 112 ^c	D 142	D 292 ^d
Screening 5 weeks	Lead-in 1 week	On treatment 4 months							Follow-up	
	Placebo	Treatment A : 10 mg QD (daily) Treatment B : 20 mg QW (weekly) Treatment C : Placebo QD								

^a MRI, MRE, and DXA baseline scans should be performed approximately 21 days prior to the Day 1 dose. Eligibility should be confirmed by central imaging lab prior to entry into the lead-in period (Day -7).

^b The Day 86 visit is scheduled 4 weeks (+1 Day) after the Day 57 visit, to tie in with a PK assessment.

^c MRI, MRE and DXA end of treatment scans are conducted at Day 112 (+/- 1 week).

^d DXA follow-up scan and immunogenicity sample collection are conducted 6 months (+/- 2 weeks) after the last dose.

D = Day

Physical examinations, vital sign measurements, 12-lead electrocardiograms (ECG), clinical laboratory evaluations, MRI, MRE and DXA scans will be performed at selected times throughout the study. Subjects will be closely monitored for adverse events throughout the study. Blood will be collected for pharmacokinetic (PK) and pharmacodynamic (PD) analysis. Approximately 500 mL of blood will be drawn from each subject during the study.

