For each subject, the total scheduled study duration from Screening to last Follow-up visit is approximately 12 months, comprised of screening (Day -42 to Day -8), placebo lead-in (Day -7 to Day -1), on-treatment (Day 1 to Day 112) and a wash-out follow-up (Day 113 to Day 142) period, plus a scheduled follow-up visit that will be performed approximately 6 months (Day

292) after the last dose to perform DXA scanning and an additional immunogenicity measurement. Of note, subjects with a positive result in the ADA and/or anti-FGF21 antibody assays at the Day 142 and/or Day 292 follow-up visits, and who do not have evidence of decreasing or stable antibodies, will be followed for up to 12 months after the D142 visit until antibody levels resolve or demonstrate a consistent decreasing trend (these immunogenicity follow-up visits will be conducted approximately every 6-8 weeks).

The end of the study is defined as the date of the last scheduled follow-up visit or immunogenicity follow-up visit, whichever is later, of the last subject in the study.

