Targeted PE		X	A targeted physical exam should be performed by the investigator or qualified professional. It includes assessment of heart, lung, abdomen and injection site reactions (as measured by the Draize Scale for erythema and edema (see Section 5.3.3) and should also be guided by the examiner's observations and/or patient complaints on new or changed conditions,

Table 5.1-1: Screening Procedural Outline (MB130045)

Procedure	Screening	Lead-in	Notes
	D-42 to D-8	D-7	
			symptoms or concerns.
Physical Measurements	X	X	Weight, BMI and waist circumference measurement. See Section 5.9 Height at screening only.
Vital Signs	X		Includes body temperature, respiratory rate, seated blood pressure and heart rate. Blood pressure and heart rate should be measured after the subject has been seated quietly for at least 5 minutes.
Electrocardiogram (ECGs)	X		ECGs should be recorded after the subject has been supine for at least 5 minutes. ECG parameters including QTcF will be collected on the CRF.
IVRS Call	X	X	IVRS call to be conducted on the day of each subject visit where indicated
Laboratory Tests (hematology, clinical chemistry, urinalysis, INR)	X		Subjects are required to fast for at least 10 hours prior to the collection of specimens for clinical laboratory tests.
Pregnancy Testing	X		Female subjects of child bearing potential. Serum pregnancy testing performed at screening
██████████	█		
Lipid panel	X		Triglycerides, total cholesterol, LDL and HDL
FSH	X		In women <55 years, to confirm menopause.
Clinical Drug Supplies			
Dispense Lead-in supply		X	
Review injection technique		X	
Adverse Event Reporting			
Monitor for Non-Serious Adverse Events		X	All non-serious AEs will be collected from the start of the Lead-In phase until 30 days after discontinuation of dosing. AEs should be followed to resolution or stabilization.
Monitor for Serious Adverse Events	X	X	All SAEs must be collected from the date of subject's written consent until 30 days after discontinuation of dosing. In addition, the investigator should report any SAE that occurs after 30 days post-dosing that is believed to be related to study drug or protocol-specified procedure

Abbreviations: D = Day

Table 5.1-2: On Treatment Procedural Outline (MB130045)

Procedure	D 1	D 15	D 29	D 43	D 57	D 86	End of Treatment D 112	Early Termination Visit ^a	Notes
Clinic Visit Window (days)	0	+3	+3	+3	+3	+3	-3		

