Patient diary review	X	X	X	X	X	X	X	X	
^a Early Termination is not a scheduled visit. For early termination PK and PD assessments, refer to Table 5.5.1-1 Abbreviations: D = Day									

Table 5.1-3: Post Treatment Follow-up Procedural Outline (MB130045)

Procedure	D 142 (30 days after last dose)	D 292 (6 mo after last dose)	Follow-up for immunogenicity ^a (up to 12 months post Day 142)	Early Termination Visit ^b	Notes
Visit Window	+/- 3 days	+/-2 wk	n/a		
IVRS Call	X			X	
Safety Assessments					
Physical Examination	X			X	
Targeted Physical Examination					Injection site reactions (as measured by the Draize Scale for erythema and edema (see Section 5.3.3), others as clinically indicated. See note in Screening procedures.
Physical Measurements	X			X	Weight (using calibrated scale), BMI and waist circumference measurement.
Vital Signs	X			X	See note in screening procedures.
Electrocardiograms (ECGs)	X			X	See note in screening procedures.
Laboratory Tests (hematology, clinical chemistry, urinalysis, INR)	X			X	See note in screening procedures.
Pregnancy Testing	X			X	Female subjects of child-bearing potential. Urine pregnancy testing to be performed at post treatment specified visits with reflex to serum if urine pregnancy testing is positive.
Dual-emission X-ray Absorptiometry (DXA)		X			Bone imaging (hip and lumbar spine) at all imaging facilities.
Adverse Event Reporting					
Monitor for Adverse Events	X			X	Up to 30 days after the last dose.
Monitor for Serious Adverse Events	X			X	See note in screening procedures.
Pharmacokinetic (PK) Assessments					
PK Sampling	X	X			Refer to Table 5.5.1-1
Immunogenicity testing	X	X	X	X	Refer to Table 5.5.1-1 and Section 5.7
████████████████████	██████████				
██████████	██████████				

^a Applies only to subjects with positive immunogenicity at D142 and/or D292. (Refer to [Section 5.7](#)). These immunogenicity follow-up visits will commence after D142 or D292, if immunogenicity results are positive at D142 or D292, respectively, without evidence of decreasing or stable antibodies.

^b Early Termination is not a scheduled visit. For early termination PK and PD assessments, refer to [Table 5.5.1-1](#)

Abbreviations: D = Day

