6.1.1 Serious Adverse Event Collection and Reporting

Sections 5.6.1 and 5.6.2 in the Investigator Brochure (IB)⁷ represent the Reference Safety Information to determine expectedness of serious adverse events for expedited reporting. Following the subject's written consent to participate in the study, all SAEs, whether related or not related to study drug, must be collected, including those thought to be associated with protocol-specified procedures. All SAEs must be collected that occur during the screening period and within 30 days of discontinuation of dosing. If applicable, SAEs must be collected that relate to any later protocol-specified procedure (e.g., a follow-up skin biopsy).

The investigator should report any SAE that occurs after these time periods and that is believed to be related to study drug or protocol-specified procedure.

An SAE report should be completed for any event where doubt exists regarding its seriousness.

If the investigator believes that an SAE is not related to study drug, but is potentially related to the conditions of the study (such as withdrawal of previous therapy or a complication of a study procedure), the relationship should be specified in the narrative section of the SAE Report Form.

SAEs, whether related or not related to study drug, and pregnancies must be reported to BMS (or designee) within 24 hours. SAEs must be recorded on the SAE Report Form; pregnancies on a Pregnancy Surveillance Form (electronic or paper forms). The preferred method for SAE data reporting collection is through the eCRF. The paper SAE/pregnancy surveillance forms are only intended as a back-up option when the eCRF system is not functioning. In this case, the paper forms are to be transmitted via email or confirmed facsimile (fax) transmission to:

SAE Email Address: Refer to Contact Information list.

SAE Facsimile Number: Refer to Contact Information list.

For studies capturing SAEs through electronic data capture (EDC), electronic submission is the required method for reporting. The paper forms should be used and submitted immediately, only in the event the electronic system is unavailable for transmission. When paper forms are used, the original paper forms are to remain on site.

SAE Telephone Contact (required for SAE and pregnancy reporting): Refer to Contact Information list.

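### After about Day 142, new non-serious AEs and SAEs not judged related are not routinely collected, although every subject returns at Day 292 for bone and antibody safety measurements

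*Protocol*

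**What the plan says.** **Collection windows.** For non-serious events, Protocol Table 5.1-1 states: "All non-serious AEs will be collected from the start of the Lead-In phase until 30 days after discontinuation of dosing". The AE row of Table 5.1-3 carries the note "Up to 30 days after the last dose". For serious events, section 6.1.1 states: "All SAEs must be collected that occur during the screening period and within 30 days of discontinuation of dosing". Beyond that, Table 5.1-1 adds only that "the investigator should report any SAE that occurs after 30 days post-dosing that is believed to be related to study drug or protocol-specified procedure". In Table 5.1-3 both AE rows are marked at Day 142 and at early termination. Neither is marked at Day 292 or at the immunogenicity follow-up visits.

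**Late visits.** Sections 1.5.1 and 3.1 bring every subject back at Day 292, about six months after the last dose, for DXA and an antibody sample. Subjects who are antibody-positive at Day 142 or Day 292, without decreasing or stable antibodies, return about every 6-8 weeks for up to 12 months after Day 142.

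**Statements pointing the other way.** Section 3.1 says: "Subjects will be closely monitored for adverse events throughout the study". It counts the Day 292 visit in each subject's scheduled duration of about 12 months, and adds: "The end of the study is defined as the date of the last scheduled follow-up visit or immunogenicity follow-up visit", whichever is later, for the last subject. Section 6.2.1 says when collection of non-serious events starts but not when it stops. Section 1.5.1 says that clinically relevant immune reactions considered related will be reported as AEs, and gives no time limit.

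**The concern.** The late visits exist because of risks that the protocol itself leaves open. Section 1.5.1 says: "The clinical consequences of a neutralizing anti-drug antibody (ADA) response to endogenous FGF21 are unknown". It gives rash and fever as examples of events to watch for, and schedules the six-month DXA to see whether any effect on BMD persists. Safety and tolerability belong to the primary objective, and BMD is among the safety endpoints in section 8.3.1 and SAP section 4.2.

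At these visits the schedule provides for the laboratory or imaging measurement but prompts no adverse-event enquiry. A late antibody titre or BMD change could then be reported without a systematic record of whether the subject had a reaction or a fracture in the months before. If late events reach the database mainly when an investigator already believes they are related, the record for a risk of unknown consequence leans towards showing nothing. Sites also cannot follow both section 3.1 and Tables 5.1-1 and 5.1-3.

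**Working it through.** **Inputs**
- Treatment and washout (Protocol section 3.1): "on-treatment (Day 1 to Day 112) and a wash-out follow-up (Day 113 to Day 142) period", so the last scheduled dose is on Day 112.
- Routine AE window: last dose + 30 days (Tables 5.1-1 and 5.1-3, section 6.1.1).
- Late visit for all subjects: Day 292, +/- 14 days (Table 5.1-3, section 5.3.1.1).
- Extended antibody follow-up: up to 12 months after Day 142, taken here as 365 days.
- First-in-human antibody rate: 3 of 72 (section 1.5.1).
- Active-arm subjects: 2 x 30 = 60 (section 3.1).

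**Step 1. Reproduce the plan's own timing**
- 112 + 30 = 142, matching the label of Day 142 as 30 days after the last dose.
- 292 - 112 = 180 days, or about 5.9 months, matching the label of 6 months.

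**Step 2. Gap for all subjects**
- Uncovered days: 292 - 142 = 150.
- Share of post-dose time uncovered: 150/180 = 83%. Covered: 30/180 = 17%.
- With the visit window: 278 - 142 = 136 days to 306 - 142 = 164 days.

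**Step 3. Ceiling for extended antibody follow-up**
- Latest day: 142 + 365 = 507. This day is derived and is not printed in the documents.
- Post-dose time: 507 - 112 = 395 days. Uncovered: 507 - 142 = 365 days, and 365/395 = 92%.
- Number of subjects: assuming the first-in-human rate, 60 x 3/72 = 2.5 antibody-positive subjects. The exact 95% interval for 3/72 is 0.87% to 11.7%, or 0.5 to 7.0 of 60.
- This counts all positives. Only those without decreasing or stable antibodies enter extended follow-up, and all three first-in-human positives had falling titres. At that rate 2.5 is therefore an upper figure for the subgroup.

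**Step 4. What can still be captured after Day 142**

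| Route | Limit |
|---|---|
| Later SAEs (Table 5.1-1, section 6.1.1) | Only if believed related to study drug or a protocol procedure |
| Immune reactions (section 1.5.1) | Only if considered related; no time limit, but no prompt in Table 5.1-3 |
| AEs already open (Table 5.1-1, section 6.2.1) | Followed to resolution or stabilization; new events not covered |
| Unscheduled assessments (section 5.9.3) | Investigator's discretion |
| Significant worsening on a safety assessment (section 6.7) | No time limit, but weak for bone: section 5.10 withholds post-screening imaging results from sites |
| Deaths (SAP section 7.6.1) | All reported deaths listed; does not reach rash, fever or fracture |

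No row gives a scheduled, causality-neutral question about new events at Day 292 or later.

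**The case against.** The strongest reply is that the schedule is a deliberate choice with a basis in the protocol. Section 3.3.1 equates five half-lives with 30 days, so the AE window covers washout. Section 3.1 gives Day 292 a limited purpose. The primary objective concerns 16 weeks of dosing, and the SAP on-treatment period ends 14 days after the last dose, so the main safety results would not change. This stands, and it is why the point concerns the interpretation of late safety data only.

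A reader might infer that AE collection stops completely and that the trial cannot record any clinical consequence of antibodies or bone change. The documents do not support that. Related SAEs stay reportable without a time limit, immune reactions considered related are to be reported as AEs, and the other routes in the table remain. Nor do empty table cells prove that a site asks nothing: section 6 accepts spontaneous reports.

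A reader might also infer that this trial could not match the first-in-human statement that all three antibody-positive subjects were in good health with no AEs reported. The documents do not say how AEs were collected in that follow-up, so the comparison cannot be made.

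Day 507 and the 92% describe a ceiling for a conditional subgroup that may be very small or empty. The documents give no fracture or late-event rate from which to estimate missed events.

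The sentence in section 3.1 could be read as general narrative that yields to the tables. Even so, the protocol does not say which governs, and section 6.2.1 leaves the stop date open.

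**Conclusion.** The point holds as a limited gap plus an inconsistency. New non-serious AEs, and SAEs not judged related to study drug or a protocol procedure, have no routine collection after about Day 142. For every subject who completes dosing on schedule that leaves 150 of the 180 days to Day 292 (136 to 164 days with the visit window). For a few antibody-positive subjects it could extend to 365 of 395 days at most. Late capture is not absent, but it rests largely on causality judgement or discretion, for risks whose consequences the protocol calls unknown.

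The day counts assume a last dose on Day 112 and 12 months of 365 days. The reading of Table 5.1-3 does not depend on its layout alone, because the written notes and section 6.1.1 state the 30-day limit. The point is a cheap improvement to late safety data. It does not affect sample size, power, type I error or the efficacy analysis.

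**What to change.** 1. **Reconcile the text.** Align Protocol sections 1.5.1, 3.1, 6.1.1 and 6.2.1 with Tables 5.1-1 and 5.1-3, so that one rule states what is collected after 30 days post-dose and until when.
2. **Schedule the enquiry.** In Table 5.1-3, mark the AE and SAE rows at Day 292 and at each immunogenicity follow-up visit.
3. **Define the content.** By open-ended questioning, as section 6 requires, collect all SAEs regardless of causality, plus non-serious possible immune reactions and bone events including fracture, until the subject's last visit.
4. **Separate the reporting.** SAP section 6.1 already defines a follow-up period, but section 7.6.3 tabulates AEs from the first active dose without an end point. State there that these late events are listed and counted separately as follow-up-period events, so that on-treatment rates are unchanged.

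**Cost.** Table and wording changes and a few more CRF entries at visits already planned. The drawbacks are recall of up to about 150 days at Day 292 and some background events unrelated to treatment. Separate reporting by arm, with placebo alongside, keeps the background events interpretable but does not remove the recall problem.

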5.1.1 Retesting During Screening or Lead-in Period

Retesting of laboratory parameters and/or other assessments within any single Screening or Lead-in period will be permitted (in addition to any parameters that require a confirmatory value).

Any new result will override the previous result (i.e., the most current result prior to Randomization) and is the value by which study inclusion will be assessed, as it represents the subject's most current, clinical state.

5.2 Study Materials

Supplied by the site:

The site will provide all required materials for the tests performed locally (i.e., relevant clinical laboratory tests and urine drug screens). The site will have available a well-calibrated scale for recording body weight, a 12-lead ECG machine, and a calibrated sphygmomanometer and thermometer for vital signs assessments. The site will have a centrifuge (refrigerated, if possible), a monitored and alarmed refrigerator, and freezer (-20°C or below, -70°C preferred), as well as containers and dry ice for shipment and storage of blood samples. The site will provide all materials required for accurate source documentation of study activities and for housing the subjects during the study.

Supplied by the Central Lab

The Central Lab will supply the Laboratory manual, tubes and labels for collection of samples.

Supplied by the Central Imaging Lab

The central imaging lab will supply the Imaging manual(s) for MRI for hepatic fat fraction, MRE for liver stiffness, DXA scanning and, if applicable, phantoms.

Supplied by the Sponsor

BMS will provide a BMS-approved protocol and any amendment(s) or administrative letter(s) (if required), an Investigator Brochure, electronic case report forms, patient education training materials and subject supplies to support subcutaneous injections, site support tools and forms study drug logs, emergency contact cards and patient diaries.

5.3 Safety Assessments

5.3.1 Safety Imaging Assessment for the Study

Image acquisition guidelines and submission processes will be outlined in the MB130045 Imaging Manual, to be provided by the central imaging lab.

A central imaging lab will perform all imaging analyses.

The clinical site will be trained in imaging procedures prior to scanning the first study subject. Images will be submitted to the central imaging lab for central review. The site will be informed of quality issues or needs for repeat scanning via queries from the central imaging lab.

Any incidental findings of potential clinical relevance that are not directly associated with the objectives of the protocol should be evaluated and handled by the Study Investigator as per standard medical/clinical judgment.

